8.6.4 Point of enrolment

Subjects are enrolled into the clinical investigation when they have signed the Patient Informed Consent Form prior to Pre-implant assessment Visit 1 (Pre1).

8.6.5 Expected duration of the clinical investigation

From first enrollment of the first subject to final assessment at Visit 3 of the last enrolled subject the total expected duration is 4 years.

8.6.6 Expected duration of each subject's participation

The expected duration for each subject from enrolment is 20 months (+/- 1 month).

8.6.7 Number of subjects required to be included in the clinical investigation

The number of subjects to be enrolled will be **N=100** subjects across the seven investigator implant sites.

In view of possible attrition rate of 5 to 10 % of enrolled subjects, randomly lost to follow up during the course of the study any time after enrolment, all subjects enrolled will be included in the final analysis as the “intention to treat” cohort with the majority being assessed “as per protocol”.

The number of subjects recruited per site will reflect the local normal practices for treatment in the elderly population during the study enrolment time frame of 24 months. The study will aim to accrue subjects distributed across all study sites and languages to avoid site and cultural bias.

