8.2.1 Preimplant visit 1 = Pre1

Preimplant visit 1 corresponds to the first evaluation with the full assessment battery for each subject before surgery and corresponds to his/her absolute baseline.

- Preimplant assessment before implant surgery date \leq 2 months

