8.2.2 Postimplant Visit 2 = Post1

Postimplant Visit 2, (Post 1) corresponds to the first assessment after implantation @ 12 months (+/- 1 month) post surgery.

- Postimplant assessment post surgery @ 12 months + 1 month.

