8.6 Subjects

8.6.1 Inclusion Criteria

- Unilateral CI candidates with bilateral postlingual deafness with intention to treat
- ≥ 60 years at *first* unilateral cochlear implant
- Implant ear: meets all local criteria for CI treatment
- Contralateral ear: average pure tone thresholds indicate a moderately-severe to profound hearing loss (4 freq. average: 0.5, 1, 2 and 3 or 4 kHz >56 dBHL).
- Willingness to participate in and to comply with all study procedures
- Fluency in languages used to assess clinical performance
- Appropriate expectations from routine CI treatment
- Able to decide on study participation personally and independently sign their consent

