7.1 Handling of Dropouts or Missing Data

All participants should be included in the analysis regardless of missing values and no imputation (for example, last value carried forward) should be utilised. All possible care should be taken to ensure that missing values are not encountered at baseline especially with respect to subgroups of interest. The analysis methods to be suggested in the following section take into account all available data and produce unbiased estimates of effect even in the presence of missing values.

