7.3 Statistical Analyses

Primary hypothesis analysis

If comparison between the HUI3 multi-attribute score from pre-surgery to only one follow-up time point is of interest then paired t-tests can be used. A check of the assumption that the change from pre-surgery is normally distributed should be performed. The distribution of change scores should be approximately symmetric. The disadvantage of this approach is that it uses only complete data at any given pair of time points

If all pairwise differences are of interest (as per the hypothesis) and the scatter plot of change over time appears (close to) linear then a linear mixed-effects model with a fixed effect of time (treated as a continuous variable) and a random effect for participant should be used to explain the change in response variable over time. Tukey pairwise differences between time points can be specified (we recommend using the *multcomp* package in R as it does not require balanced designs i.e. the same sample size across time points). Appropriate diagnostic checks of the linear mixed-effects model (for example, normality of the residuals, normality of the random effects) should always be undertaken. An advantage of the linear mixed-effects model is that it uses all available data even for subjects who have dropped out at a given time point and then returned.

If the change over time was evidently not linear from the scatterplot of response against time then alternative approaches should be used. For example:

1. A quadratic or cubic term for time could be added to the linear mixed-effects model and checked to determine if that improves the fit of the model (eg via reduced AIC, better diagnostic checks).
2. The pre-surgery HUI3 multi attribute score value can be used as a predictor variable (with the response variable then only including the post-surgery visits). A significant coefficient would imply that the amount of change is dependent on the pre-surgery score. An interaction between baseline score and post-surgery time points could also be included – this would show whether the change in mean score over time is impacted by baseline score. This approach will remove any participant without baseline data from the analysis.

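### Subjects are enrolled at consent and all are analysed, so a candidate who is assessed at Pre1 but never implanted stays in the mixed model for change after implantation; the likely effect is small and its direction is unknown

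*Protocol*

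**What the plan says.** Protocol 8.6.4 settles when a person counts as a study subject: "Subjects are enrolled into the clinical investigation when they have signed the Patient Informed Consent Form prior to Pre-implant assessment Visit 1 (Pre1"). Under 8.6.1, those enrolled are "Unilateral CI candidates with bilateral postlingual deafness with intention to treat", so they are candidates and not yet recipients. Pre1 is the "first evaluation with the full assessment battery for each subject before surgery" (8.2.1). Both follow-up visits are counted from the operation; Post1, for example, "corresponds to the first assessment after implantation @ 12 months (+/- 1 month) post surgery" (8.2.2).

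Protocol 8.6.7 expects 5 to 10% of enrolled subjects to be lost at random at some time after enrolment. It then says that "all subjects enrolled will be included in the final analysis as the" intention-to-treat cohort, most of them assessed per protocol. The per-protocol set is not defined.

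SAP 7.1 follows the same line: "All participants should be included in the analysis regardless of missing values and no imputation (for example, last value carried forward) should be utilised". For the all-pairwise primary hypothesis, SAP 7.3 prescribes a linear mixed-effects model because "it uses all available data even for subjects who have dropped out at a given time point". That sentence goes on to mention subjects who come back, but the model keeps any subject with at least one observation.

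Neither document says what happens to someone enrolled and then not implanted. Protocol sections 8.6.3 and 17 cover withdrawal and declining health but do not name this case.

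**The concern.** The primary objective is change in HUI3 following CI treatment, with each subject as his or her own control. A subject who has Pre1 and no surgery carries no information on that change. SAP 7.1 relies on the model giving unbiased estimates despite missing values. For this subject, however, the 12-month post-surgery value is not missing; it does not exist. The mixed model treats the two situations alike.

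The random-loss premise in 8.6.7 is also less secure for this group than for ordinary loss to follow-up, because not reaching surgery may be related to health or to preference. With a single arm there is no allocated comparison for an intention-to-treat rule to protect. At stake is whether the reported gain describes the implanted population or a slightly different mixture.

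**Working it through.** **The plan's own figures.** SAP section 5 uses a change of 0.10, SD of change 0.25, 90% power and a paired t-test. Exact noncentral-t power gives 68 subjects at two-sided 0.05 (power 90.2%) and 88 at 0.05/3 = 0.0167 (power 90.3%). Both match the SAP and are not in dispute.

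**Inputs for the shift.** None of these three is given in the documents.
- f, the share of subjects with a Pre1 record who are never implanted: assumed 5-10%. This borrows the all-cause attrition range in protocol 8.6.7, so it is generous for this one cause.
- d, the mean Pre1 HUI3 of the never-implanted minus that of the implanted: assumed -0.20 to +0.20.
- r, the within-subject correlation of HUI3: assumed 0.4-0.6.

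**Formulas** (random intercept, visit as a category, Pre1 observed in all):
- The Pre1 mean moves by f × d.
- Each fitted postimplant mean moves by r × f × d, because the random effect predicts the absent visits from Pre1.
- The estimated change therefore differs from the change in implanted subjects by r × f × d - f × d = -(1 - r) × f × d.

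**Results for the change from Pre1.**

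| f | d | r | Pre1 mean | Post means | Change |
|---|---|---|---|---|---|
| 5% | -0.10 | 0.5 | -0.005 | -0.0025 | +0.0025 |
| 5% | -0.20 | 0.4 | -0.010 | -0.004 | +0.006 |
| 10% | -0.20 | 0.6 | -0.020 | -0.012 | +0.008 |
| 10% | -0.20 | 0.4 | -0.020 | -0.008 | +0.012 |
| 10% | +0.20 | 0.4 | +0.020 | +0.008 | -0.012 |

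The range is -0.012 to +0.012, and the shift is zero when d = 0. The extreme is 0.012/0.03 = 40% of the clinically significant change and 0.012/0.10 = 12% of the design target.

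**Linear time.** The SAP's first-listed mixed model treats time as continuous. I refitted with visits at 0, 12 and 18 months, f = 10%, d = -0.20, r = 0.4 and an illustrative gain of 0.10 at both follow-ups. The shift is about 0.009 at 12 months and 0.013 at 18 months. About 0.004 also enters the 12-to-18-month contrast. With visit as a category that contrast is unaffected, because both post means move equally.

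**Other summaries.** Raw visit means (SAP 7.2) have no postimplant shift to offset the baseline one, so their difference moves by -f × d, at most 0.10 × 0.20 = 0.02 in size. The paired t-test and the option with baseline as predictor are not affected, because Pre1-only subjects contribute nothing to either.

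**Power if only implanted subjects are analysed** (change 0.10, SD 0.25, paired test):

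| Subjects analysed | α = 0.05 | α = 0.0167 |
|---|---|---|
| 95 | 97.1% | 92.6% |
| 90 | 96.4% | 91.0% |
| 85 | 95.4% | 89.1% |
| 80 | 94.2% | 86.8% |

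The last two rows apply only if non-implantation comes on top of the planned attrition.

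**The case against.** The case against making much of this is good, and most of it stands.

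- The entry criteria require that the ear to be implanted meets local candidacy criteria. They also exclude medical contraindications to surgery, severe dependence or fragility, and candidates who fail on dementia or depression. This removes many who would drop out before surgery for poor health, so both f and a large negative d are likely to be limited. With SD of change 0.25 and r = 0.4, the implied HUI3 SD is 0.25/√1.2 = 0.23, so d = 0.20 is nearly 0.9 SD.
- A reader might infer that the gain is overstated. The documents do not support a direction: someone who declines surgery may be in better health, and the gain would then be understated.
- A reader might infer that the never-implanted affect only the preimplant mean. That is true of raw visit means, which the SAP treats as preliminary description. In the mixed model the fitted post means move the same way and offset part of the shift.
- A reader might infer that the SAP sets two conflicting analyses on the primary hypothesis. It does not. The paired t-test is offered only when a single follow-up is of interest; for all pairwise differences the mixed model is directed.
- The intention-to-treat wording in 8.6.7 can be read simply as an instruction not to discard people lost to follow-up. That principle is sound and should be kept for implanted subjects.

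What the objection does not remove is that the written rule admits people who never had the treatment to an estimate of change after it, and that nothing in either document says how to handle them.

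**Conclusion.** The point holds as a minor defect in the definition of the analysis set. As written, a candidate with Pre1 and no implant enters the primary mixed model. Under the stated assumptions the estimated change moves by no more than 0.012 either way with visit as a category, or about 0.013 at 18 months with linear time. At f = 5%, d = -0.10 and r = 0.5 the shift is 0.0025. These figures rest wholly on assumed f, d and r. Someone who leaves before Pre1 adds no data and causes no shift. Nothing here suggests that the primary conclusion would change or that the sample size is inadequate. The reason to act is that the analysed population should match the objective, and the correction is cheap.

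**What to change.** In protocol 8.6.7 and SAP 7.1, define the primary analysis set as all enrolled subjects who undergo implant surgery, whatever their later device use, follow-up or missing visits. Do not add a requirement for a Pre1 HUI3: it would drop implanted subjects with postimplant data only, whom SAP 7.1 now keeps, and it has nothing to do with non-implantation. Let this definition replace the intention-to-treat label, and either define the per-protocol set or remove the reference to it. List subjects enrolled but not implanted separately, with their Pre1 values and reasons, and state the number implanted beside N=100.

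The cost is a few sentences, with no new data or patients. The analysed number may fall slightly below 100. To keep the SAP's 88 after a 10% loss takes 88/0.90 = 97.8, or 98 enrolled, so N=100 still suffices for the planned attrition. If non-implantation is additional to it and leaves 80-85 subjects, power at 0.0167 is about 87-89%.

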8.6.8 Estimated time needed to select this number (i.e. enrolment period)

Thirty-one months from first to last (100th) patient enrolled at Visit 1 in 8 implant clinics.

8.7 Procedures

As an observational study, there will be no change in the treatment of the hearing impaired patient's hearing loss compared to local routine practices. When the patient agrees to participate as a subject in the study, a set of data related to their outcomes from the routine hearing treatment will be gathered for the purposes of the study.

The dataset gathered is composed of outcomes from routine audiological and geriatric assessments that are completed by experienced professionals at the clinic, as well as self-assessments via questionnaires completed by the patient directly and with assistance as needed.

A detailed list of the evaluations performed, the data gathered and guidelines for administration of questionnaires are described in a separate document *“Procedure document”*.

8.8 Monitoring Plan

The monitoring schedule and documents viewed are detailed in a separate document *“Monitoring Plan”*.

9 Statistical Considerations

For primary, secondary and tertiary study objectives an Intra subject endpoint comparison is used: All pairwise comparisons are of interest i.e. preimplant to 12 months postimplant, preimplant to 18 months postimplant, and the change from 12 to 18 months.

The power analysis applied for the study design was based on an available data set (n= 67, Cochlear-IROS data) of repeated measures on the HUI3, collected for elderly CI-patients, at preimplant and 12 months post implant intervals. The HUI 3 will serve as the primary outcome measure for this study to measure the added health utility gain for the multi- attribute health status from preimplant (@ \leq 2 months first activation) to the postimplant (@ 12 months post activation) interval in a population of implanted 60+ year olds.

The minimum clinically important change over two intervals for the HUI3 is 0.03 units on a scale of 0 representing poor health and 1.0 representing full health.

The power calculations were performed using the free package G*Power 3.1 by a consultant statistician at the Macquarie Sydney University.

The differences observed for the implanted elderly population in the existing Cochlear IROS dataset demonstrated a mean change = 0.165 at 95% confidence interval, with a range of 0.109 to 0.221 and a non-normal distribution for the cohort of 67 implanted elderly recipients over the age of 60 years examined.

Using this information to estimate the sample size required for significant changes on the HUI3 multi attribute score, *for intra subject comparisons of endpoints*, aiming for a change of \geq 0.10 units between the two test intervals, and a power of 90% and using a two-side paired t-test to calculate the 5% significance level, a sample of N=68 is required for the multi-attribute health utility. For comparison of changes in self ratings individual health domains of the HUI3, aiming for a power of 80% a sample of N=100 is required.

Study statistical analysis plan is available as separate document.

10 Data Management

Data collection will be performed using eCRFs within a validated and verified electronic data capture system (EDC) with role based security and unique login credentials for each individual user. Site personnel will be trained on the completion of the eCRFs. The investigator will confirm data accuracy by providing an electronic signature.

Data will be collected, stored and analysed in a secure manner in compliance with 21 CFR Part 11 and privacy regulations.

The EDC has built-in edit checks and will generate automated data clarification forms (DCFs). The clinical project manager (CPM), monitor and data manager may review the data for medical, scientific and data integrity, and will create manual DCFs where appropriate. Responses to DCFs will be entered into the EDC, with updates to the study data where required.

Following completion of the study, investigators will be provided with the data for their site (e.g. on a CD-ROM) for national and site specific archiving requirements.

After the final clinical investigation report (CIR) has been approved the data will be stored on CD-ROM and archived with the trial master file at the sponsor's site. The data are stored for a period of 15 years.

11 Amendments to the Observational Study Protocol (CIP)

No changes in the study procedures shall be effected without mutual agreement of the investigator(s) and the Sponsor. All changes must be documented by a signed (CIP)

amendment. Substantial changes that impact the patient experience during the trial will require notification to the responsible Ethics Committee(s).

12 Deviations from the Observational Study Protocol

As an observational study, it is recommended that the investigator comply with the protocol as far as possible for all enrolled subjects. Protection of the subjects' rights, safety, privacy and well-being is always paramount throughout the study and at any time. Deviations to the study protocol shall be documented and reported to the Sponsor as soon as possible. The EC should be informed by the investigator as applicable.

13 Device accountability

Routine procedures for commercially implanted device registration and accompanying warranty are to be followed.

14 Statements of compliance

14.1 Declaration of Helsinki and compliance with standards

The observational study shall be conducted in accordance with the ethical principles that have their origin in the most recent version of the Declaration of Helsinki (2013 or later), the EN ISO 14155:2011 and any regional or national regulations, as appropriate. The study will be registered on ClinicalTrials.gov.

14.2 Ethics Committee and Competent Authority Approval

Each clinic wishing to collaborate and publish their data must obtain Ethics Committee (EC) Approval/Opinion (or Competent Authority (CA) Approval if applicable) for their participation in the study and obtain formal approval prior to enrolling the first subject locally.

The observational study shall not commence prior to the written favourable opinion or approval from the EC and or CA (if appropriate) is obtained.

The investigator shall submit the final version of the observational study protocol, the patient informed consent (PIC) and all subsequently required documents to the Ethics Committee. A copy of the Ethics Committee opinion/approval shall be provided to the sponsor. A copy of the EC approval shall be retained in the clinic for the locally dictated time requirements.

Sponsor and investigator shall continue the communication with the EC as required by national regulations, the observational study protocol, or the responsible EC.

Any additional requirements imposed by the EC or CA shall be followed.

The investigator shall submit the appropriate documentation if any extension or renewal of the EC approval is required. In particular substantial amendments to the observational study protocol, the informed consent, or other written information provided to subjects must be approved in writing by the EC.

The investigator will report to the EC any new information that may affect the safety of the subjects or the conduct of the observational study. The investigator shall send written status summaries of the observational study to the EC regularly as per local EC requirements.

Upon completion of the observational study, the investigator shall provide the EC with a brief report of the outcome of the observational study as per local EC requirement.

The observational study is covered by a clinical trial insurance meeting the requirements of the participating countries. National requirements are specified in the national patient informed consent (PIC).

14.3 Audits and Supervision

Study sites and study documentation may be subject to Quality Assurance audits during the course of the observational study. In addition, regulatory bodies at their discretion may conduct inspections, during and after study completion.

14.4 Study Records

The investigational site will receive and has to maintain an Investigator's File which does include without limitation at a minimum the signed Observational Study protocol, the EC approval letter, the CA approval letter (if applicable), completed Patient Informed Consent Forms, Investigator copies of all CRFs, correspondence with the Sponsor and third parties (if applicable) related to the Study, a subject identification list, and a site delegation and signature sheet. All study records and defined source documents shall be archived at the investigational centre for at least 15 years after the end of the study.

15 Patient Informed Consent (PIC) process

15.1 Obtaining informed consent

The investigator must obtain written informed consent from the subject prior to any study related examination or activity, and after explaining the rationale for and the details, aims and objectives of the study, the risks and benefits and alternative treatments, and the extent of the subject's involvement. Ample time must be provided for the subject to inquire about details of the observational study and to decide whether to participate. All questions about the observational study should be answered to the satisfaction of the subject or the subject's legally acceptable representative. Subjects must not be coerced or unduly influenced to participate or to continue to participate in the study.

Each subject and the person who conducted the informed consent discussion must sign and date the patient informed consent form. Where required, a witness must sign and personally date the consent form.

A copy of the information leaflet and consent form must be given to the subject. All signed Informed Consent Forms must be archived in the Investigator's File at the investigational site, according to the requirements of the country's health regulations, after completion of the observational study.

The subject or the subject's legally acceptable representative must be informed in a timely manner if new information becomes available that may be relevant to the subject's willingness to continue participation in the observational study. The communication of this information must be documented.

The investigator shall forward any amendment made to the approved subject informed consent for review to the Sponsor or Study Monitor and any other written information to be provided to the subject, prior to submission to his EC.

